# **General questions:**

Do you have an 'all-favourite' bandage that you find easier to apply?	Yes No N/a
Which one do you prefer? Why?	Name brand:

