# **Study Protocol**

# **Project summary**

This study aims to provide explanations of when, for whom and in what circumstances are two different types of compression bandages (paste or dry) selected in the treatment of lower limb ulceration.

Compression bandages are used in the treatment of leg ulceration. A leg ulcer develops when blood vessels are not working as they should; they are painful, distressing and have a considerable impact on quality of life. They require frequent dressing changes, but with correct treatment can heal within three months. Evidence that compression is the gold standard to heal leg ulceration exists, but comparative data between different brands of compression bandages does not. Selection of a compression system is often based on nurses' preference, based on their acquired knowledge and skills of product application. This study aims to understand when, for whom and in what circumstances two very different product types should be selected to treat individual patient's lower limbs.

Patients have been the primary inspiration for this project. They often report that they are unable to tolerate compression bandages and when questioned in more detail, it appears that different systems have not been considered.

This study will use a research technique called 'realist evaluation', which acknowledges that leg ulcer care is complex, and is undertaken in a complex health care system. The process commences with listing what we think is happening (initial theories) and refine this through the analysis until the most plausible explanation is found.

The study is divided into two concurrent parts:

Patients who require bilateral compression bandages (registered with a Newcastle upon Tyne GP) will be selected from the caseload of District Nurses and Ambulatory Clinics.

- Opinions on the ease of application will be sought from Community Nurses and District Nurses who are applying the compression bandages to the recruited patients
- (ii) Opinions on comfort will be sought from the recruited patients.

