#### Research question and study aim

This research asks: 'When, for whom and in what circumstances are two different types of compression bandages selected in the treatment of lower limb ulceration?'

This study aims to provide explanations of when, for whom and in what circumstances are two different types of compression bandages selected in the treatment of lower limb ulceration. The premise is that all systems under review in this study work equally well, but it is unclear which system works best in the right patient, at the right time and in the hand of the right clinician.

The secondary objectives are to add to the body of knowledge that pertains to leg ulceration care and guide staff to select the right compression bandage for each patient.

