# Data analysis

# **Refining Programme Theories**

Excel/word documents will be used to store data. The data collected from the recruited participants will be analysed collectively, using descriptive statistics where appropriate and inductively bringing together the various data sources in emerging themes. This will demonstrate how theories evolve in the course of the study. Engagement, involvement, and collaboration between each member of the research team will take place to refine theories to understand when, for whom and in what circumstances are two different types of compression bandages selected in clinical practice. It is hoped and expected that at the end of the study, new guidance for nursing staff will be developed to guide the selection of compression bandages.

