# **APPENDIX 3. PATIENT AND NURSE'S EXPERIENCE** PATIENT AND NURSE QUESTIONNAIRE – CLINICAL EXPERIENCE

Bandage used: Right Leg S1F/S1R, S2F/S2R or S3F/ S3R (circle what applies)	S1F = UrgoK2 S1R = UrgoK2 Lite S2F = Coban2 S2R = Coban2 Lite S3F = AndoFlex TLC Calamine S3R = AndoFlex TLC Lite Zinc
FOR THE PATIENT TO COMPLETE	
Please rate the following as your overall experience of circle):	of wearing this bandage (please
Has this bandage helped with your pain?	Yes No N/a
Has this bandage improved your comfort?	Yes No N/a
Has this bandage improved your ability to wear normal footwear and clothes?	Yes No N/a
Has this bandage stayed in place?	Yes No N/a
Has this bandage improved your skin condition?	Yes No N/a
Has this bandage improved your skin irritation?	Yes No N/a
Please add any further comment of your personal experience	
FOR THE NURSE TO COMPLETE	
Prior to last bandage application, was the leg washed with Hydromol mixed in warm water?	Yes No N/a
Prior to last bandage application, was the leg debrided using a debridement cloth or tenatome?	Yes No N/a
Looking at the leg, has this bandage helped improve the leg's skin condition?	Yes No N/a
Looking at the leg, has this bandage reduced the leg's skin irritation?	Yes No N/a
Looking at the leg, has this bandage helped with wound healing?	Yes No N/a

Looking at the leg, has this bandage helped with wound

malodour?

Yes

No N/a

	S1F = UrgoK2
	S1R = UrgoK2 Lite
Bandage used: Left Leg	
	S2F = Coban2
S1F/S1R, S2F/S2R or S3F/ S3R (circle what applies)	S2R = Coban2 Lite
	S3F = AndoFlex TLC Calamine
	S3R = AndoFlex TLC Lite Zinc

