# NURSE QUESTIONNAIRE – PROFESSIONAL OPINIONS ON APPLICATION

	S1F = UrgoK2		
	S1R = UrgoK2 Lite		
Bandage used: Right Leg			
	S2F = Coban2		
S1F/S1R, S2F/S2R or S3F/ S3R (circle what applies)	S2R = Coban2 Lite		
	S3F = AndoFlex TLC Calamine		
	S3R = AndoFlex TLC Lite Zinc		
On a scale of 1-6 (1 = worst, 6 = best) please rate the following as your overall			

On a scale of 1-6 (1 = worst, 6 = best) please rate the following as your overall clinical experience of using this compression system compared to previously used compression system (please circle):

How easy is it to apply? (i.e. speed, technique required such as simple spirals and visual indicators for correct tension, cutting, tapes)	1	2	3	4	5	6	
How easy is it to remove? (i.e. Wear time – appearance of the bandage post wear – slippage, unwind, worn out areas)	1	2	3	4	5	6	
How 'neat' does it look once it has been applied?	1	2	3	4	5	6	
Is it easy to learn how to apply it?	1	2	3	4	5	6	
Is it easy to teach others to apply?	1	2	3	4	5	6	
Do you like using this bandage			Yes	No N/a	a		

	S1F = UrgoK2
	S1R = UrgoK2 Lite
Bandage used: Left Leg	
	S2F = Coban2
S1F/S1R, S2F/S2R or S3F/ S3R (circle what applies)	S2R = Coban2 Lite
	S3F = AndoFlex TLC Calamine
	S3R = AndoFlex TLC Lite Zinc

On a scale of 1-6 (1 = worst, 6 = best) please rate the following as your overall clinical experience of using this compression system compared to previously used compression system (please circle):

compression system (preuse en cie).							
How easy is it to apply? (i.e. speed, technique required such as simple spirals and visual indicators for correct tension, cutting, tapes)	1	2	3	4	5	6	
How easy is it to remove? (i.e. Wear time – appearance of the bandage post wear – slippage, unwind, worn out areas)	1	2	3	4	5	6	
How 'neat' does it look once it has been applied?	1	2	3	4	5	6	
Is it easy to learn how to apply it?	1	2	3	4	5	6	
Is it easy to teach others to apply?	1	2	3	4	5	6	
Do you like using this bandage			Yes	No N/a	a		

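### The nurse favourite-bandage item merges preference with ease of application, and may steer or filter the only open question put to nurses

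*Protocol*

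**What the plan says.** The research question (Protocol, Research question and study aim) is "When, for whom and in what circumstances are two different types of compression bandages selected in the treatment of lower limb ulceration". The Project summary names nurse preference as a driver of selection: "Selection of a compression system is often based on nurses' preference, based on their acquired knowledge and skills of product application".

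Under General questions, at the end of Appendix 3, the nurse is first asked "Do you have an 'all-favourite' bandage that you find easier to apply", answered Yes, No or N/a. The next line asks "Which one do you prefer? Why" and gives a field for the brand.

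The other nurse items in Appendix 3 are closed and concern the bandage on each leg:

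- The form on application has five 1–6 ratings per leg and the Yes/No/N/a item "Do you like using this bandage".
- The clinical experience form asks about skin condition, irritation and healing, for example "Looking at the leg, has this bandage helped with wound healing".

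The planned analysis is descriptive and thematic: "using descriptive statistics where appropriate and inductively bringing together the various data sources in emerging themes".

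**The concern.** A closed question should ask one thing, and a question about reasons should not follow a prompt that supplies one. The first general question breaks both rules.

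This matters more here than in most questionnaires. Under Compression bandage selection procedure, sealed envelopes decide which leg gets paste and which gets dry, so the choice between types is not observed within the study. What nurses say about their preferences is therefore a main source on why they select one type over the other. If the wording tilts those statements towards ease, the programme theories may give ease more weight than nurses would have given it unprompted. The study expects to turn those theories into guidance for nursing staff.

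**Working it through.** The Protocol gives no figure on this point, so there is none to reproduce. The check is a reading of every nurse-completed item in Appendix 3 against the research question and the analysis section.

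**Step 1: what the closed answer can mean.** Two separate facts are folded into one reply.

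| Nurse's position | Clear answer? |
|---|---|
| Has a favourite, and it is the easiest to apply | Yes |
| Has a favourite, but for another reason | None: No hides the preference, Yes counts it as ease |
| No overall favourite, but finds one easier to apply | None: Yes and No are each half right |
| No favourite, and none is easier | No |

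Two of the four positions have no correct reply. A count of Yes or of No mixes positions that cannot be separated afterwards from the closed item alone.

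**Step 2: where else a nurse can state a preference and a reason.** The liking item ("Do you like using this bandage") does not mention ease, but it concerns the allocated bandage and asks for no reason. The skin, irritation and healing items are ratings of the allocated bandage, not preferences. Patients have a free-comment line on their part of the form; nurses have none. The follow-up "Which one do you prefer? Why" is therefore the only open nurse question in Appendix 3. No nurse item asks for which patients or circumstances a bandage is preferred, although that is the research question.

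**Step 3: how the first item bears on the follow-up.** The follow-up sits directly below the closed item, and its 'which one' can be read as referring back to the favourite just described as easier to apply. Four of the five rated items before it are also about ease (applying, removing, learning, teaching); the fifth is about neatness. A nurse who has answered No or N/a may take the follow-up as not applicable. No instruction says whether to skip it or complete it.

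**Step 4: size.** Let p be the share of nurses whose favourite is not the easiest to apply, and q the fraction of those who leave the follow-up blank. The share of nurses whose preference goes unrecorded is p × q. This runs from 0 (when q = 0) to p (when q = 1). The Protocol gives neither p nor q. It also says that the number of nurses cannot be estimated. Priming of the answers that are given would come on top and cannot be quantified either.

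**The case against.** The strongest defence has four parts.

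- **The follow-up is neutral.** It does not mention ease, asks for the reason, and has no skip rule. A nurse can write that patients tolerate the bandage better, and inductive analysis can use that. This stands. A reader might infer that every preference not based on ease is lost or relabelled, and might illustrate it with a 60/40 split in which the 40% vanish. The documents do not support that: it needs q = 1 in the expression above, which assumes the loss it is meant to show.
- **The item fits its form.** The form is headed as opinions on application, and the Project summary says "Opinions on the ease of application will be sought from Community Nurses and District Nurses". This stands in part. An ease item on an ease form is reasonable, but the item asks for an overall favourite, which is wider than ease, and the study names preference as a driver of selection.
- **Views other than ease are collected elsewhere.** Nurses rate skin, irritation and healing per leg, and patients report pain, comfort and skin. This stands as evidence about how bandages perform. It does not tell the analyst why a nurse would choose one.
- **The item does not simply repeat the study's premise.** A reader might infer that it can only confirm what the Project summary already assumes. That summary speaks of acquired knowledge and skill, which are not the same as ease, so this inference fails.

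None of this removes the ambiguity of the closed item or its position ahead of the open question.

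**Conclusion.** The point holds as a defect in the wording of one item. The closed question is double-barrelled and leading, so its answers cannot be interpreted for nurses whose favourite is not the easiest to apply. It may also prime or filter the only open question put to nurses in Appendix 3. That it is double-barrelled follows from the text alone. The effect on the follow-up is a plausible risk, which rests on nurses reading the two lines as linked, and its size cannot be derived from the Protocol. Whether the reason has its own answer space cannot be judged from the extracted form, and nothing here depends on it. The item should be reworded because the data cannot be repaired later and the change costs very little.

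**What to change.** Remove the clause about ease from the first general question and ask in neutral terms: *Is there a bandage you usually prefer? Which one? Why, and for which patients or circumstances?* State on the form that every nurse completes the open part, including those who report no usual preference.

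Nothing is lost, because ease of application is already rated per leg on the preceding form. The cost is a revised form and a slightly longer open answer. If any forms have been completed with the present wording, record which version each nurse answered and do not pool the two versions of the closed item.
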